## 272 **9. Analysis of the Primary and Secondary Efficacy Endpoints**

273           The primary analysis will include both the pediatric and adult participants in a single analysis.  
274           All analyses comparing the BP aspart/lispro with the Control Group will follow the intention-to-  
275           treat (ITT) principle with the data from each participant analyzed according to the treatment  
276           assigned by randomization. Participants not randomized due to a protocol deviation and  
277           assigned to the BP Group will be analyzed according to the BP group assignment and a  
278           sensitivity analysis will be performed reanalyzing these participants as part of the Control group.

279

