- 1585 ○ Percentage change in the TDD of insulin over the first two-week period relative to
1586 the TDD of insulin in last two-week period (iLet Group only)

1587 Weight and Body Mass Index (BMI)
1588 From the weekly questionnaires, number of hypoglycemic events requiring carbohydrate
1589 treatment per 24 hours
1590 From the weekly questionnaires, grams of carbohydrate taken specifically to treat
1591 hypoglycemic events per 24 hours

1592 **11.5 CGM Metrics Calculations**

1593 Baseline values for each CGM metric will be computed from either the participant's personal
1594 Dexcom G6 data or from the G6 wear prior to randomization. The most recent two weeks of
1595 CGM data prior to randomization will be included in the calculation of baseline CGM metrics.
1596 During the RCT, CGM metrics will be calculated from the CGM data collected from the Control
1597 Group for comparison with the CGM data from the BP Group. Percentage of CGM values that
1598 fall within a specified range will be calculated by dividing the number of CGM values that fall
1599 within the range by the total number of CGM readings.

1600 **11.6 Analysis of the Primary and Secondary Efficacy Endpoints**

1601 The primary analysis will include both the pediatric and adult participants in a single analysis.
1602 All analyses comparing the BP aspart/lispro with the Control Group will follow the intention-to-
1603 treat (ITT) principle with the data from each participant analyzed according to the treatment
1604 assigned by randomization.

1605 A per-protocol analysis that includes participants adhering to the protocol will be performed and
1606 detailed in the SAP. Sensitivity analyses on the primary and key secondary outcomes also will
1607 be described in the SAP.

1608 **11.6.1 HbA1c Analyses (Superiority)**

1609 HbA1c at 13 weeks will be compared between the BP aspart/lispro and Control Groups using a
1610 linear mixed effects regression model adjusting for baseline HbA1c, age, and clinical center

1611 (random factor). HbA1c is expected to be normally distributed, but regression diagnostics will
1612 be performed to check the residuals and an appropriate alternative transformation or a
1613 nonparametric analysis based on ranks will be performed if the residuals have a skewed
1614 distribution. In the event that some HbA1c values are not available at 13 weeks, then the linear
1615 mixed effect regression model will use the method of direct likelihood to incorporate information

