220 Percentage of time CGM is used will be calculated as the amount of time of CGM readings  
221 divided by the total possible time the participant could have used the CGM (end date-time minus

222 start date-time from the analysis window tables in Section 7.1). Note that this denominator  
223 includes sensor warm up periods with no CGM values, so this metric will serve as a conservative  
224 estimate of CGM use.

225

226 Mean of daily differences is the mean of the absolute differences between daily mean glucose.

227 **7.3 Closed Loop Use**

228 For calculating closed loop use, the numerator will be number of hours in which the CL insulin  
229 delivery system was on and available, and the denominator is the period end date-time minus  
230 start date-time. Note the denominator includes time in which the pump is turned off or not in use,  
231 thus this metric would reflect a real-world percentage of time in which the participant actively  
232 used the device.

233

234 **8. Description of Statistical Methods**

235 **8.1 General Approach**

236 For all outcomes, mean and standard deviation or summary statistics appropriate to the  
237 distribution will be reported.

238

239 All p-values will be two-sided. Standard residual diagnostics will be performed for all analyses.  
240 If residuals are highly skewed, then an appropriate alternative transformation or nonparametric  
241 analysis based on ranks will be performed instead.

242

243 All analyses will compare the BP with aspart/lispro group with the Control Group.

244 **8.2 Analysis Cohorts**

245 *Primary and Secondary Analyses:*

- 246 • All randomized participants and participants assigned to an RCT treatment group will be  
247 analyzed for the intention-to-treat (ITT) efficacy analyses and all safety analyses.
- 248 • Safety outcomes will be reported for the pre-randomization period for all enrolled  
249 participants.

250

251 *Per Protocol Analysis:*

- 252 • A per-protocol analysis will be restricted to participants with:
  - 253 a) Baseline and 13-week HbA1c central lab measurements available,
  - 254 b) For participants in the Control Group, at least 80% of CGM data available in the 13-week  
255 RCT wear period defined in Section 7.1,

256           c) No glucose-lowering medications used other than those acceptable in the protocol,  
257           d) No major protocol deviation that could impact outcome measures, and  

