258           e) For participants in the BP group, closed loop mode is active for at least 80% of the time  
259           during the 13 weeks and announce a meal bolus on average at least 2 times per day when  
260           the system is being used.

261           This analysis will only involve the primary and key secondary outcomes and will only be done if  
262           >5% of subjects are excluded based on this criterion.

263

264 *While-on-Treatment Analysis:*

- 265           • A while-on-treatment analysis will include all participants assigned/randomized to an RCT  
266           treatment group. For participants who discontinued the iLet device in the BP group, HbA1c  
267           and CGM metrics will only include data prior to iLet discontinuation.

268

269           This analysis will only involve the hierarchical outcomes. Any missing endpoints will be handled  
270           by the method of direct likelihood.

271

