375 of the BP Group was that of the Control Group.
  - 376 ○ Available cases only.
- 377 • The primary analysis will be recalculated switching non-randomized participants  
378 assigned to the BP Group due to a protocol deviation to the Control group.

380 **9.6 Questionnaires and Other Outcomes Analyses**

381 Questionnaire scoring will be detailed in the Questionnaire Scoring Appendix.

382 Summary statistics of total and subscale scores appropriate to the distribution will be tabulated  
383 by visit and treatment group. For questionnaires administered to both randomization groups,  
384 comparisons will be made using similar linear models as described above for the primary and  
385 key secondary outcomes. If questionnaires include a total score, separate models will be run for  
386 the total score and any subscales, with the exception of the Clarke Hypoglycemia Awareness  
387 questionnaire. The models for comparing DTSQ scores between treatment groups will use a  
388 combined score calculated as the DTSQ-S score plus the DTSQ-C score. It will still adjust for  
389 the baseline DTSQ-S score.

390  
391 Similarly, for carbohydrate, total daily insulin, weight and BMI metrics, comparisons will be  
392 made using similar linear models as described above for the primary HbA1c analysis (Section  
393 9.1). Percentage change in the TDD of insulin over the first two-week period relative to the TDD  
394 of insulin in the last two-week period will not be tested because this metric is limited to BP  
395 group only. A 95% confidence interval will be reported for treatment group mean difference in  
396 total daily insulin, body weight, and body mass index.

397

398 **10. Safety Analyses**

399 All randomized participants will be included in the safety analyses and all of their post-  
400 randomization safety events will be reported. Separately, any adverse events occurring between  
401 screening and randomization will be reported.

402

403 All reportable adverse events will be tabulated by treatment group. Details will be provided in a  
404 listing of each event, including Medical Dictionary for Regulatory Activities (MedDRA) term  
405 and MedDRA System Organ Class. Safety analyses for the RCT will include events occurring  
406 on or after randomization until and including the 13-week visit, latest contact date, or Day 98  
407 from randomization, whichever occurs first. Analysis windows for the RCT and other periods are  

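### Non-randomized participants are counted in the BP arm of the set called ITT, SAP 2 does not declare this, and no planned analysis is limited to randomized participants

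*SAP*

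**What the plan says.** Protocol 11.6 words its rule as the intention-to-"treat (ITT) principle with the data from each participant analyzed according to the treatment" received through randomization. It makes no exception. Protocol 3.3 describes one route to a group assignment, through entry of the Randomization Visit data on the study website.

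SAP 8.2 defines the set for the ITT efficacy analyses more widely: "All randomized participants and participants assigned to an RCT treatment group will be" analyzed. SAP 9 repeats the protocol rule and then adds the exception, which runs on over three lines: "assigned by randomization. Participants not randomized due to a protocol deviation and" "assigned to the BP Group will be analyzed according to the BP group assignment and a" "sensitivity analysis will be performed reanalyzing these participants as part of the Control group". SAP 9.5 gives that run a narrower scope: "The primary analysis will be recalculated switching non-randomized participants" from BP to Control.

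The other planned populations are:

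- While-on-treatment (SAP 8.2): "A while-on-treatment analysis will include all participants assigned/randomized to an RCT" group.
- Per-protocol (SAP 8.2): criterion (d) requires "No major protocol deviation that could impact outcome measures, and" other conditions. The analysis covers the primary and key secondary outcomes only, and is done only if more than 5% of subjects are excluded.
- Missing-data sensitivity runs (SAP 9.5): multiple imputation and available cases, with no exclusion of non-randomized participants.

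SAP 2 declares consistency with the protocol's statistics chapter apart from one change, that the two BP groups will not be pooled. The revision history records, at version 3.0 during enrollment, that sensitivity analyses for the non-randomized participants were added.

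**The concern.** A participant placed in BP without randomization has no randomized counterpart in Control. Adding such people to one arm only means that the comparison is no longer wholly protected by randomization, whatever the set is called. The handling is stated openly in SAP 9 and was in place before unblinding, so it is neither hidden nor post hoc. Two gaps remain. SAP 2, where a reader looks for departures from the protocol, does not mention it. And no planned analysis estimates the randomized comparison.

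The switch run does not fill the second gap, because it moves these people into the Control mean instead of removing them. Efficacy is declared on HbA1c superiority alone (SAP 6.1), and there the switch run is a good stress test: it is harsher than exclusion whenever these participants do better than Control. For non-inferiority on time <54 mg/dL it is not necessarily conservative, and SAP 9.5 as worded may not apply it to that endpoint at all.

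**Working it through.** **Inputs.** From SAP 5: 200 BP and 100 Control completers; HbA1c difference 0.4 and SD 0.8; time <54 margin 1 and SD 2.0; baseline correlation 0.40. One-sided alpha is taken as 0.025, as SAP 9.2 describes (SAP 5 prints 0.025%). The number of non-randomized participants, k, is not in the documents; 1, 5 and 10 are assumed.

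**The plan's own figure.** The planning SE is SD × √(1 − 0.40²) × √(1/200 + 1/100).

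- HbA1c: 0.8 × 0.9165 × 0.1225 = 0.0898.
- Time <54: 2.0 × 0.9165 × 0.1225 = 0.2245.

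Both ratios (0.4/0.0898 and 1/0.2245) are 4.45. Power from the noncentral t with n₁ + n₂ − 3 degrees of freedom is 99.3% for each endpoint, in line with the stated >99% and 99%.

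**Shift formulas.** Let B and C be the randomized BP and Control means and m the mean of the k non-randomized participants. Relative to the randomized difference B − C:

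- main run (k counted in BP): shift = k(m − B)/(200 + k)
- switch run (k counted in Control): shift = −k(m − C)/(100 + k)

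**HbA1c.** Assume these participants are 0.5 points better than randomized BP after adjustment. This is a large gap: 0.5/(0.8 × 0.9165) = 0.68 residual SD. With the planned effect, B − C = −0.4, so m − B = −0.5 and m − C = −0.9.

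| k | Main run, shift in favour of BP | As % of SE 0.0898 | Switch run, shift toward zero |
|---|---|---|---|
| 1 | 0.5/201 = 0.002 | 3% | 0.9/101 = 0.009 |
| 5 | 2.5/205 = 0.012 | 14% | 4.5/105 = 0.043 |
| 10 | 5/210 = 0.024 | 27% | 9/110 = 0.082 |

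If instead these participants were exactly like randomized BP (m = B), the main run would be unbiased, but the switch run would still shrink 0.4 to 0.4 × 100/105 = 0.381 at k = 5. It is a stress test and not an estimate of the randomized comparison.

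**Time <54 mg/dL.** Here a larger B − C is unfavourable to BP. Both shifts are negative, so both runs understate the difference, exactly when C < m < B. In that case the main-run error cannot exceed k(B − C)/(200 + k). The largest unfavourable insulin-only difference in the documents is in Protocol A.1.4, monitored arms: 1.55 − 1.32 = +0.23 points. That figure is for time <60 mg/dL, used here as a stand-in. At +0.23 the bound is 0.23/201 = 0.001, 1.15/205 = 0.006 and 2.3/210 = 0.011 for k = 1, 5 and 10. The last is 0.011/0.2245 = 5% of the SE and about 1% of the margin. With m midway between the arms:

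| k | Randomized difference | Main run | Switch run |
|---|---|---|---|
| 5 | 0.230 | 0.230 − 0.575/205 = 0.227 | 0.230 − 0.575/105 = 0.225 |
| 10 | 0.230 | 0.230 − 1.15/210 = 0.225 | 0.230 − 1.15/110 = 0.220 |

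If m lies outside the range of the two arm means, the shifts have opposite signs and the two runs bracket the randomized difference.

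**Power of a randomized-only run.** By the same method: 99.3% at 200 or 190 vs 100, and 99.2% at 180 vs 100, for each endpoint.

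**The case against.** The strongest reply is that the plan already protects the decision.

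- *The per-protocol run will probably happen and will probably drop these people.* SAP 3 expects about 220 + 110 = 330 participants and SAP 5 expects 300 completers, so 30/330 = 9% do not complete. That alone would probably pass the 5% trigger, since a 13-week HbA1c is required. Non-randomization is itself called a protocol deviation. This stands in part: the trigger is likely to be met. But criterion (d) does not name these participants, and the set also drops people on adherence and data completeness. It is a different population, and it covers only two of the ten endpoints.
- *The efficacy endpoint is covered.* For HbA1c the switch run guards against bias in the sponsor's favour. That stands.
- *The time <54 argument is one-sided.* It needs BP to be the higher arm. The +0.23 comes from one earlier study with short arms and a different device generation, and the unmonitored arms of that study favour BP (1.66 vs 1.95). In the mirror case, with BP lower and m between the arms, both runs move the difference upward, which is conservative. This is correct; the other insulin-only results against usual care also favour BP. The unfavourable case is possible, not expected, and small.
- *Protocol 11.6 is silent on people with no randomized assignment, and SAP 8.2 and 9 define the set openly.* The definition is indeed open. But the protocol's rule gives these people no place in either arm, so adding them is a departure that SAP 2 should list.

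**Conclusion.** The concern holds. The set labelled ITT includes people who were not randomized, SAP 2 does not declare it, and none of the planned runs is restricted to randomized participants. The numerical effect is probably small. Over assumed k of 1 to 10, the HbA1c main estimate moves by 0.002 to 0.024 points if these participants are 0.5 points better than randomized BP. The time <54 error is at most 0.011 against a margin of 1 when their mean lies between the arms and BP is 0.23 higher. Both k and the 0.5-point gap are assumptions without a source in the documents, and nothing here shows that a conclusion would change. The issue is which population the pivotal result describes. The change should be made because it is cheap and removes the question.

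**What to change.** - **SAP 9.5:** add a randomized-only analysis of the primary, key secondary and other hierarchical endpoints. Alternatively, make that set the ITT set and add the non-randomized participants as BP in a sensitivity analysis.
- **Switch run:** keep it, and state which endpoints it covers, since SAP 9 can be read more broadly than SAP 9.5.
- **SAP 2:** list the departure from Protocol 11.6.
- **Label and wording:** do not call the combined set ITT without qualification. Align the population wording in SAP 8.2, 9, 9.5 and 10; the last two speak only of randomized participants, which does not contradict 8.2 but is uneven with it.
- **Reporting:** keep these participants in the safety reporting, labelled as non-randomized. Give their number and the reasons in the flow chart and protocol-deviation table already planned in SAP 11.
- **Fiasp SAP:** its Section 6 adopts the same analyses, so say there whether the added run applies to Fiasp vs Control.

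The cost is SAP wording and one extra run per hierarchical endpoint. No new data are needed.

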### **9.1 HbA1c Analyses (Superiority)**

280           Only lab HbA1c measurements will be used in the analyses. If a hemoglobin variant is present  
281           such that the primary central lab is unable to measure HbA1c using its methodology, the sample  
282           may be analyzed at a separate lab using the boronate affinity method or another method which is  
283           not affected by the hemoglobin variant. Summary statistics appropriate to the distribution will be  
284           reported for HbA1c at baseline, at 6 weeks, and at Week 13 as well as for differences from  
285           baseline by treatment group. If both venous and capillary central lab measurements are available  
286           for the same timepoint, the venous value will be used in the analyses. Scatterplots of the baseline  
287           HbA1c vs. week 13 HbA1c and baseline HbA1c vs. change in HbA1c will be produced for the  
288           Control and BP aspart/lispro groups.

289

290           HbA1c at 13 weeks will be compared between the BP aspart/lispro and Control Groups using a  
291           linear mixed effects regression model adjusting for baseline HbA1c, age, and clinical center

292 (random factor). A 95% confidence interval will be reported. HbA1c is expected to be normally  
293 distributed, but regression diagnostics will be performed to check the residuals and an  
294 appropriate alternative transformation or nonparametric analysis based on ranks will be  
295 performed if the residuals have a skewed distribution. In the event that some HbA1c values are  
296 not available at 13 weeks, then the linear mixed effect regression model will use the method of  
297 direct likelihood to incorporate information from baseline and 6 weeks measurements to  
298 calculate the maximum likelihood at 13 weeks. Further details on direct likelihood are provided  
299 in Section 15.

300

### 301 **9.2 Time <54 mg/dL (Noninferiority)**

302 Summary statistics appropriate to the distribution will be reported for % time <54 mg/dL at  
303 baseline and over the 13-week follow-up period as well as for differences from baseline by  
304 treatment group. Scatterplots of the baseline time <54 mg/dL vs. 13-week time <54 mg/dL and  
305 baseline time <54 mg/dL vs. change in time <54 mg/dL will be produced for the Control and BP  
306 aspart/lispro groups. If % time <54 mg/dL is skewed and does not display well in a scatterplot,  
307 then boxplots will be produced instead.

308

309 Time below 54 mg/dL will be calculated over 13 weeks for each subject as described in Section  
310 7. A two-sided 95% confidence interval on the mean difference in % time <54 mg/dL between  
311 BP aspart/lispro and Control Group will be performed based on a linear mixed effects regression  
312 model adjusting for baseline % time <54 mg/dL, age, and clinical center (random factor).  
313 Noninferiority will be assessed by comparing the upper bound of this confidence interval to a  
314 noninferiority limit of 1%. Missing data will be handled by the method of direct likelihood (see  
315 Section 15). Residuals values will be examined for an approximate normal distribution. If the  
316 values are highly skewed, then an appropriate alternative transformation or nonparametric  
317 analysis based on ranks will be performed instead. A two-sided p-value will be reported, and a  
318 5% significance level will be used to declare significance.

319

320 Since noninferiority is typically framed in terms of a one-sided test, it is worth noting that the left  
321 half of a two-sided test at alpha = 0.05 gives the same rejection region as a one-sided test at alpha  
322 = 0.025. Therefore, reporting a two-sided 95% confidence interval will provide flexibility to test  
323 for inferiority if noninferiority cannot be declared while maintaining the overall type 1 error rate  
324 of 5%.

### 325 **9.3 Secondary CGM and HbA1c Metrics (Superiority)**

326 Summary statistics appropriate to the distribution will be reported for the CGM-measured  
327 metrics at baseline and during follow up as well as for differences from baseline by treatment

328 group. Scatterplots or boxplots of the secondary efficacy endpoints included in the hierarchy  
329 will be produced at baseline and over 13 weeks for the Control and BP aspart/lispro groups.  
330  
331 Secondary continuous CGM metrics will be calculated as described in Section 7. CGM metric  
332 differences between BP and Control Groups will be compared using a linear mixed effects  
333 regression model adjusting for the baseline value of the metric, age, and clinical center (random  
334 effect). A 95% confidence interval for the treatment group difference will be reported. Residual  
335 values will be examined for an approximate normal distribution. If residuals are highly skewed,  
336 then an appropriate alternative transformation or nonparametric analysis based on ranks will be  
337 performed instead. Missing data will be handled using direct likelihood (see Section 15).  
338  
339 For the binary secondary outcomes, *p*-values will be produced from logistic regression models  
340 adjusting for the same factors mentioned above for the primary analyses (i.e., baseline value of  
341 the outcome, age, and clinical center as a random effect). A 95% confidence interval for the  
342 treatment group adjusted risk difference will be produced using parametric bootstrapping.  
343  
344 Participant-level cumulative distribution plots of HbA1c and % time in range 70-180 mg/dL by  
345 treatment group will be produced.

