#### 346 **9.4 Hierarchical Analyses**

347 To preserve the overall type 1 error for the primary and key secondary efficacy endpoints as  
348 defined in Section 6.1 and additional secondary efficacy endpoints listed in Section 6.2.1, a  
349 hierarchical testing procedure will be used. If the primary analysis for HbA1c results in a  
350 statistically significant result ( $p < 0.05$ ), then testing at the 0.05 level will proceed to the next  
351 outcome metric. This process continues iteratively moving to the next variable down on the list  
352 until a non-significant result is observed, or all 10 variables have been tested. If a non-  
353 significant result is encountered, then formal statistical hypothesis testing is terminated and any  
354 variables lower on the list will not be formally tested.  
355  
356 Regardless of the results of the hierarchical testing, summary statistics appropriate to the  
357 distribution will be tabulated by treatment group for each hierarchical outcome. A 95%  
358 confidence interval for the treatment group difference also will be calculated for all hierarchical  
359 outcomes listed above. However, a confidence interval that excludes zero will not be considered  
360 a statistically significant result if an outcome variable higher on the hierarchical list failed to  
361 reach statistical significance.

362 **9.5 Sensitivity Analyses**

- 363 • Covariate Adjustment: The primary analysis includes a pre-specified list of covariates. As  
364 an additional sensitivity analysis, any baseline demographic or clinical characteristics  
365 observed to be imbalanced between treatment groups will be added as covariates to the  
366 analyses of the primary endpoint. The determination of a meaningful baseline imbalance  
367 will be based on clinical judgment and not a p-value.
- 368 • Missing Data: All randomized participants will be included in the primary and key  
369 secondary analyses according to ITT and any missing data will be handled using direct  
370 likelihood. It is worth emphasizing that any statistical method for handling missing data  
371 makes a number of untestable assumptions. The goal will be to minimize the amount of  
372 missing data in this study so that results and conclusions will not be sensitive to which  
373 statistical method is used. To that end, the following methods will be performed:
  - 374 ○ Multiple imputation with a pattern mixture model assuming the dropout trajectory  

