408 further detailed in Section 7.1.

409

410 Formal statistical testing only will be performed for selected safety endpoints. For the following  
411 outcomes, mean and standard deviation (SD) or summary statistics appropriate to the distribution  
412 will be tabulated by treatment group and formal statistical comparisons will be performed if there  
413 are enough events (at least 5 events combined between the BP aspart/lispro and Control Group):

- 414 • Number of SH events and SH event rate per 100 person-years
- 415 • Number of DKA events and DKA event rate per 100 person-years
- 416 • Other serious adverse events
- 417 • Worsening of HbA1c from baseline to 13 weeks by >0.5%

418

419 If enough events occur for the severe hypoglycemia (SH), DKA, and other serious adverse event  
420 (SAE) outcomes, the numbers of events will be compared between the two treatment groups  
421 during the RCT using a Poisson regression model adjusting for baseline age and HbA1c, and site  
422 as a random effect. For SH, the model will additionally control for whether or not the participant  
423 experienced at least 1 SH event prior to randomization. For DKA, the model will additionally  
424 control for whether or not the participant experienced at least 1 DKA event prior to  
425 randomization. If distribution is zero-inflated or the variance is greater than its mean, then a  
426 zero-inflated Poisson or negative binomial regression model will be considered. For worsening  
427 of HbA1c from baseline to 13 weeks by >0.5%, a logistic regression model adjusting for baseline  
428 age and HbA1c and site as a random effect will be used to compare the two treatment groups.

429

430 Since the Control Group is not provided with a study blood glucose meter or blood ketone meter,  
431 no treatment group comparisons of meter data will be performed. Additionally, no formal  
432 statistical comparison will be made of all reported adverse events combined since there are

433 specific requirements in the protocol for reporting certain events in real-time for the BP Group  
434 but not the Control Group, and adverse device effects are only reported for the BP Group.

435

436 No adjustments for multiple comparisons will be made for any safety analyses.

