## 580 **15. Direct Likelihood**

581 The direct likelihood method uses baseline data to estimate missing 13-week values via  
582 maximum likelihood. This involves adding a visit variable and a treatment by visit interaction  
583 effect to the model. The baseline version of the outcome will be included as part of the outcome  
584 (i.e. not as a fixed effect covariate), but the treatment effect will be constrained to be zero at  
585 baseline. Other baseline covariates added to the model will be treated as fixed effects.

586

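### The logistic models for binary HbA1c outcomes have no missing-data rule and, fitted as written, would leave out anyone without a 13-week HbA1c; the resulting bias can go either way

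*SAP*

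**What the plan says.** **Who is analysed.** SAP 8.2: "All randomized participants and participants assigned to an RCT treatment group will be" analysed for ITT efficacy and for safety. SAP 10 repeats that all randomized participants enter the safety analyses.

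**Continuous outcomes.** SAP 9.1 handles a missing 13-week HbA1c by direct likelihood, using the baseline and 6-week values. In SAP 9.3 the paragraph on continuous CGM metrics ends with "Missing data will be handled using direct likelihood (see Section 15". SAP 13.2 extends the method to subgroup analyses. The general sentence in SAP 7.2 concerns missing CGM metrics only.

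**Binary outcomes.** The next paragraph of SAP 9.3 says that p-"values will be produced from logistic regression models", whose covariates are the baseline value of "the outcome, age, and clinical center as a random effect). A 95% confidence interval for the" adjusted risk difference then comes from a parametric bootstrap. For worsening "of HbA1c from baseline to 13 weeks by >0.5%, a logistic regression model adjusting for baseline" age and HbA1c, with site as a random effect, is specified in SAP 10. No missing-data rule appears in either place.

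**How direct likelihood is built.** SAP 15: "The baseline version of the outcome will be included as part of the outcome", so baseline is a response and not a covariate.

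**Sensitivity analyses.** SAP 9.5 lists "Multiple imputation with a pattern mixture model assuming the dropout trajectory" of the BP Group matched that of Control, and an available-cases analysis. Its missing-data item is framed around the primary and key secondary analyses.

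**The concern.** A logistic model with one outcome record per person and baseline as a covariate has no contribution from a person whose outcome is missing. Direct likelihood cannot simply be read into it. SAP 15 places baseline in the response vector, whereas the logistic models place it on the right-hand side. Improvement and worsening are changes from baseline, so they have no baseline version to put in the response vector.

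The consequence is that mean HbA1c would be analysed on all randomized participants, while the HbA1c responder rates, the HbA1c/CGM composites and the worsening test would be analysed on those with a 13-week sample, all under the same ITT description. A 6-week HbA1c available for a participant who later withdraws would be used in the first analysis and not in the others.

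Worsening is one of four safety outcomes listed for formal testing. The responder endpoints are exploratory, but none carries the flag that would keep it out of the primary manuscript. The trial is open-label, and Control participants must complete all visits to be offered the iLet extension (Protocol 4.1.2 and 5.3). Reasons for leaving may therefore differ between arms.

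**Working it through.** **1. Inputs from the documents** (SAP 3 and 5): about 220 BP and 110 Control randomized; 200 and 100 expected to complete; difference 0.4; SD 0.8; baseline correlation 0.40; two-sided 5%.

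**2. The plan's own figure.** Residual SD = 0.8 × √(1 − 0.40²) = 0.733. SE = 0.733 × √(1/200 + 1/100) = 0.0898. 0.4/0.0898 = 4.45, and 4.45 − 1.96 = 2.49, so power is 99.4%. This agrees with the stated >99%. The plan gives no rate or power for any binary endpoint.

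**3. Expected missingness.** 20/220 = 10/110 = 9.1% per arm.

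**4. Implied rates.** Assume baseline SD 0.8 and no mean change in Control. SD of change = √(2 × 0.64 × 0.6) = 0.876.
- Improvement >0.5%: BP 1 − Φ(0.1/0.876) = 45.5%; Control 1 − Φ(0.5/0.876) = 28.4%; difference 17.0 points.
- Worsening >0.5%: BP Φ(−0.9/0.876) = 15.2%; Control 28.4%; difference −13.2 points.

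**5. Reference points if those are the completers' rates.**
- BP dropouts respond at the Control rate (the SAP 9.5 control-based assumption): improvement (200/220) × 17.0 = 15.5 points; worsening (200/220) × −13.2 = −12.0. Completers then overstate by 1/0.909 − 1 = 10%.
- Logical extremes for improvement: BP dropouts all fail and Control dropouts all respond, 90.9/220 − 38.4/110 = 6.4 points; the reverse gives 24.6.
- Logical extremes for worsening: −2.9 to −21.1 points.

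**6. Simulation of the model as written.** Trivariate normal HbA1c at baseline, week 6 and week 13, with the plan's inputs and 9.1% missing per arm. Assumed: mean 7.8%, baseline-to-week-6 correlation 0.5, week-6-to-13 correlation 0.7, effect 0.3 at week 6. Dropout depends on 6-week change with log-odds 1 to 2 per SD. A baseline-adjusted logistic fit on completers, standardized to a risk difference, is compared with full data for HbA1c <7.0%, improvement >0.5% and worsening >0.5%. Positive values mean that the size of the BP benefit is overstated.

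| Dropout depends on 6-week change | Bias, % of the risk difference |
|---|---|
| In neither arm (random) | 0 |
| Equally in both arms | about −2 to +5 |
| In BP only | about +8 to +18 |
| In Control only | about −6 to −20 |

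In points, for BP only at log-odds 2, full data versus completers:
- HbA1c <7.0%: 15.0 vs 17.4 (+16%).
- Improvement: 17.2 vs 19.2 (+12%).
- Worsening: −13.2 vs −15.5 (+18% before rounding).

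At log-odds 1 the three figures are +9.8%, +8.2% and +9.4%.

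**7. Does imputation help?** Imputing continuous week-13 HbA1c from baseline and week 6 removed the bias in every scenario in which week 6 was observed. This is expected by construction, because dropout was driven by values the imputation model contains. Without a week-6 value, imputation reduces to the baseline-adjusted completers result.

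**The case against.** A reader might infer that the SAP drops every participant without a 13-week value and so inflates the device's benefit. The documents do not support that reading.

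- **Exclusion is not stated.** No sentence says that such participants are left out. Omission follows from the model form together with the silence of the text, while SAP 8.2 and 10 say that everyone is included. What stands is that the rule is unspecified and an ordinary fit would omit them.
- **Inflation is only one case.** It needs response-related dropout in BP that is not matched in Control. The mirror case understates the benefit by a similar amount, and nothing in the documents establishes which holds.
- **Doing badly on the iLet is not missingness.** Protocol 4.3 and 5.2.2 keep people who stop the device in follow-up. The SAP revision history refers to participants who stopped the iLet but continued in the study, and truncation at device stop belongs only to the while-on-treatment analysis. The week-13 window of −14 to +28 days also limits losses. The problem is confined to withdrawals and missed samples.
- **9.1% is a planning allowance,** derived from approximate enrolment and expected completers.
- **The stakes are limited.** The binary efficacy endpoints are exploratory and FDR-controlled. Continuous HbA1c already has direct likelihood and sensitivity analyses, and visit completion is tabulated by arm.

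All of this bounds the point without removing it. No planned analysis would show how far the responder or worsening results depend on the missing values.

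**Conclusion.** The gap holds as a specification fault with a conditional bias. SAP 9.3 and SAP 10 give logistic models that, fitted as written, omit participants without a 13-week HbA1c and discard any 6-week value. This sits poorly with the all-randomized statements and with the treatment of continuous HbA1c.

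At 9.1% missing, the risk difference may be unbiased, or off by up to roughly a fifth in either direction when dropout depends on response in one arm only. The size rests on the assumed mean, correlations and dropout strength; the documents supply only the difference, SD, baseline correlation and completion numbers. If actual missingness is lower, the bias shrinks with it.

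The primary endpoint and the ten-step hierarchy are not affected. The change is worth making because the worsening comparison is a formally tested safety outcome and the responder results are intended for the primary manuscript.

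**What to change.** In SAP 9.3 and SAP 10, state that binary outcomes derived from 13-week HbA1c are analysed as follows:

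1. Multiply impute the continuous 13-week HbA1c by arm from baseline, week 6, age and center. For composites, impute the CGM component as well.
2. Dichotomize each imputed data set, fit the logistic model already specified, and combine by Rubin's rules.
3. Keep the available-case logistic fit as a sensitivity analysis.
4. Extend the SAP 9.5 control-based imputation, as a sensitivity analysis, to both the responder and the worsening endpoints. This also addresses withdrawals before week 6, for whom step 1 adds little beyond baseline.
5. Report the number missing by arm for each binary endpoint.

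The BP Fiasp SAP takes its methods from this plan, so the wording would carry over.

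The cost is SAP text and modest programming, since SAP 9.5 already calls for a multiple-imputation step. No new data are needed. The small downside is reliance on an imputation model.
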